2.3.2. Inclusion Criteria

All the following criteria must be met at enrollment:

- History of non-infectious intermediate, anterior and intermediate, posterior or panuveitis in at least one eye
- Active inflammation within the last 180 days, defined by the presence of **any of the following** (in at least one eye) according to SUN criteria and the NEI vitreous haze grading scale:
 - ≥ 2+ anterior chamber cells and/or
 - ≥ 2+ vitreous haze and/or
 - active retinal or choroidal inflammation
- Active inflammation in at least one eye at enrollment, defined by **any of the following**:
 - ≥ 1+ anterior chamber cells and/or
 - ≥ 1+ vitreous haze and/or
 - active retinal/choroidal inflammation (bullous serous retinal detachment qualifies if choroidal thickening)
- **At least one** of the following criteria must be met before or at enrollment:
 - 1.) Active inflammation after 4 weeks of high-dose (1mg/kg prednisone equivalent) oral corticosteroid treatment
 - 2.) Treatment with oral corticosteroids resulting in a reduction of inflammation, followed by an increase in inflammation (of at least 1 grade in anterior chamber cells or vitreous haze or a change of non-active to active retinal/choroidal lesions) when corticosteroid is tapered, in the 180 days prior to enrollment
 - 3.) Treatment with ≥10mg/day oral prednisone or equivalent over at least the past 90 days prior to enrollment
 - 4.) Active inflammation after long-acting corticosteroid injection 4 weeks to 180 days prior to enrollment
 - 5.) One of the following uveitic conditions necessitating corticosteroid-sparing immunosuppressive treatment¹²:
 - Behcet's disease with posterior segment involvement
 - Multifocal choroiditis with panuveitis
 - Serpiginous choroidopathy
 - Birdshot retinochoroidopathy
 - Diffuse retinal vasculitis
 - Severe Vogt-Koyanagi-Harada syndrome (VKH) (for example: acute VKH that has been active for at least 4 weeks, or VKH with bullous serous retinal detachments and/or choroidal detachments with other signs of ocular inflammation)
 - Sympathetic ophthalmia
 - 6.) If the patient does not fit any of these categories, but the physician believes corticosteroid-sparing immunosuppressive therapy is indicated, eligibility may be assessed on a case-by-case basis after discussion with the coordinating center. Please contact [REDACTED] or by email.

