2.5. Definitions for primary endpoint

2.5.1. Determination of Treatment Success/Failure

Treatment success is defined as controlled ocular inflammation (see Table 2) in both eyes with 7.5 mg/day of prednisone, no periocular or intravitreal corticosteroid injections after the first 90 days of follow up, and ≤ 2 drops/day of topical 1% prednisolone acetate at the 6 month visit without treatment failure any point due to safety, tolerability or futility. Patients can stop medication at any time, but that in and of itself does not count as a treatment failure.

Table 2: Criteria for controlled inflammation

Parameter	Definition of control
Anterior chamber cells*	$\leq 0.5+$
Vitreous haze**	$\leq 0.5+$
Choroid & retina***	No active inflammation or retinal vasculitis posterior to the equator

*SUN criteria³⁰; ** NEI vitreous haze grading scale³¹ *** Cystoid macular edema is not sufficient to be called active inflammation

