< 7.5 & ≥ 5	2 – 4	1 - 2.5
< 5 & ≥ 2.5	2 - 4	1.5 - 2.5
< 2.5 & ≥ 1	2 – 4	1
0		

NOTE: When beginning Phase I (6-12 months), hold patient at 7.5 mg/day, for at least one week.

Directions for Rescue Taper

Reactivations can be mild or severe. Mild reactivations are considered an increase in inflammation up to the 1+ level in anterior chamber cell or vitreous haze. Severe reactivations are considered an increase in inflammation up to the 2+ level or higher in anterior chamber cell or vitreous haze. Retinal/choroidal lesions may be considered mild or severe at the discretion of the study physician.

If uveitis reactivates:

- Increase oral prednisone up to a dose of 1 mg/kg for severe reactivations, or for mild reactivations, up to double the dose at which the flare occurred, until uveitis is controlled. Then re-taper according to the guidelines.

Uveitis is considered non-responsive if inflammation does not increase but does not further improve after the first 4 weeks of treatment on 1mg/kg oral prednisone.

If uveitis is non-responsive:

- Hold the current dose of prednisone for an additional week. If still no improvement, treatment failure due to futility may be declared, and patients may proceed to Phase II. Alternatively, other therapies may be added, but these should be noted as a protocol deviation.
- If treatment failure is declared due to futility in Phase I, before the primary endpoint of 6 months, patients may switch to Phase II. Patients who refuse to switch to Phase II should be encouraged to return for a 6-month visit. Patients who switch to Phase II will already be followed.
- If treatment failure is declared due to futility in Phase II, before the primary endpoint of 6 months, patients will be treated according to best medical judgment. If treatment failure is declared prior to 6 months, Phase I and Phase II, every attempt must be made to bring patients back for their 6 month assessment.

After suppression of uveitis is once again achieved (either in the case of reactivation or non-response) follow the taper guidelines for Phase I. Patients who have failed the treatment to which they are randomized will then switch treatments, begin Phase II, and follow the same taper guidelines as Phase I (0-6 months). If patients flare during Phase II, they can follow directions for the rescue taper listed above. Patients who fail the second treatment at the 6 month endpoint will be treated as per the investigators discretion.

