Vitreous haze will be assessed using an indirect ophthalmoscope set at mid-power and a 20D lens. Fundus examination will be done with the last view being the area around the optic disc. The examiner should then compare this view to the photograph (Figure 1) and determine the level of vitreous haze. The National Eye Institute System for grading vitreous haze will be used for all primary and secondary outcome measures. Additionally, vitreous haze will be assessed separately on the 9-point grading scale recently published by Davis et al., known as the Miami scale. The examiner should compare the vitreous haze view with the Miami photograph. An exploratory analysis will correlate measurements from the NEI and Miami scales. Clinical measurements of vitreous haze will also be compared to objective assessments done by grading of fundus photos by the reading center.

If the physician thinks that the grading of vitreous haze is affected by a significant media opacity (i.e. a dense/mature cataract) they should indicate on the Clinical Exam Form that they cannot make a reliable judgment of vitreous haze due to the opacity.

[figure not shown]
Figure 1: National Eye Institute system for grading vitreous haze

Grade	Description
0	Clear
0.5+	Slight blurring of optic disc margin Normal striations and reflex of nerve fiber layer cannot be visualized
1+	Opacities without obscuration of retinal details
2+	Few opacities resulting in mild blurring of details of optic nerve and retinal vessels
3+	Optic nerve head and retinal vessels significantly blurred but still visible
4+	Dense opacity obscuring optic nerve head

*Grading should be conducted in a completely dark room; From Nussenblatt et al. Standardization of vitreal inflammatory activity in intermediate and posterior uveitis. Ophthalmology 1985;92:467-471.

Figure 2: Miami 9-point system for grading vitreous haze

Miami Scale for photographic grading of vitreous haze in uveitis. Am J Ophthalmol;150:637-641 e1.

Grading Retinal/Choroidal Inflammation

Assessment of active inflammation of the retina and choroid should be based on the clinical exam and ancillary testing if needed for certain diseases (i.e. fluorescein angiogram, fundus photography, B-scan ultrasound). Please refer to the table in Appendix F for imaging required for assessing uveitis activity by disease.

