5.3.4. Training and certification of ophthalmologists and study coordinators

All exams must be performed by uveitis specialists. The study protocol and classification system for grading inflammation will be reviewed by [REDACTED] (or another study ophthalmologist from [REDACTED]) with the investigators at all sites. An open-book exam on the study protocol will be administered, and a score of 80% is needed for

certification to participate in the trial. For investigators with scores less than 80%, additional instruction and a re-test will be done. Prior to study start, each site investigator will grade inflammation on 5 uveitis patients and scores will be compared to the [REDACTED] investigator's scores. If a discrepancy of greater than 1 grade in any of the measurements occurs, then additional patients will be graded until there are 5 consecutive patients where the grade is within 1 level for each of the measurements (i.e. anterior chamber cells, vitreous haze, and retinal/choroidal lesions). If both graders assess each area to have 0 inflammation in a particular patient, that patient would not count towards the 5 patients needed to complete the training. This grading assessment will be done prior to initiation of the trial and yearly thereafter. Duplicate measurements of inflammation will also be collected at the 6 and/or 12-month study visits. Inter-observer agreement will be reported.

The study protocol will be reviewed with all study coordinators by coordinating center personnel. An open-book exam on the study protocol will be administered, and a score of 80% is needed for certification to participate in the trial. For coordinators with scores less than 80%, additional instruction and a re-test will be done.

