Each of these (including the binary assessment of the presence of retinal or choroidal lesions) may be considered an ordinal variable, with relevant threshold values for each (used in determining eligibility for enrollment, or success in therapy).

Scoring of incompletely assessable eyes is governed by the following guiding principles:

1. In some patients, the front of the eye may be assessable, but the back of the eye cannot be examined and assessed clinically (even though the patient can still see out of the eye).
2. Worsening of uveitis may render it harder to assess the back of the eye, so that information cannot be considered missing at random in general.
3. Many uveitis patients have at least one eye which cannot be fully assessed, because of the progression of the disease itself. Excluding such patients or eyes completely is undesirable.
4. Treatment of uveitis will not reverse the damage which makes it difficult to assess all parts of the eye.
5. Worsening of cataracts may also cause an eye to become incompletely assessable, so that a change in assessability status does not always indicate a worsening of uveitis or a failure of uveitis treatment.

We chose the following simple, but conservative, approach to scoring such eyes. For an incompletely assessable field (anterior cells, vitreous haze, or presence of retinal or choroidal lesions) at any time, the worst value seen until that time will be assigned for the unavailable measurement. Thus, a decreasing ability to assess regions of the eye—in the absence of evidence of inflammation or uveitis criteria—does not imply failure of therapy. Decreasing ability to assess eyes which had signs of uveitis will imply failure of therapy. It is understood that this procedure will misclassify some events such as: (i) an eye which had vitreous haze or a retinal or choroidal lesion at baseline, which resolved over the course of the six months, and for which a progressing cataract rendered the posterior of the eye impossible to assess, will be scored as a failure, or (ii) an eye for which the posterior region had no inflammation at baseline, which then became impossible to assess, and then which develops posterior inflammation which cannot be seen, will be scored as a success. We believe such misclassifications will be infrequent.

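### The hands-on agreement test for examiner certification cannot detect disagreement on active retinal/choroidal lesions, one of the three components of the primary endpoint

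*Combined protocol and SAP*

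**What the plan says.** Protocol 5.3.4 has each site investigator grade 5 uveitis patients, whose scores are compared with those of a reference investigator. The exercise is done before the trial and repeated yearly. More grading is needed only under this condition: "If a discrepancy of greater than 1 grade in any of the measurements occurs". In that case "additional patients will be graded until there are 5 consecutive patients where the grade is within 1 level for each of the measurements". The measurements are listed as "i.e. anterior chamber cells, vitreous haze, and retinal/choroidal lesions". A patient in whom both graders find no inflammation in any area does not count towards the 5.

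The lesion reading is described elsewhere as follows:

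- Protocol 2.5.1, Table 2, gives the retina and choroid criterion for control as "No active inflammation or retinal vasculitis posterior to the equator". Control is required in both eyes.
- Protocol 2.3.2 defines a rise in inflammation as "at least 1 grade in anterior chamber cells or vitreous haze or a change of non-active to active retinal/choroidal lesions", which sets grades for cells and haze against a change of state for lesions.
- Protocol 5.3.2 tabulates six grades for cells and six for NEI vitreous haze. For the retina and choroid it lists no grades: "Assessment of active inflammation of the retina and choroid should be based on the clinical exam and ancillary testing if needed for certain diseases".
- SAP 3.1, on incompletely assessable eyes, treats each component as ordinal, "including the binary assessment of the presence of retinal or choroidal lesions".
- Protocol 3.2.1, in the rescue-taper directions, adds: "Retinal/choroidal lesions may be considered mild or severe at the discretion of the study physician".

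Protocol 5.3.3 provides for duplicate gradings at baseline, months 6 and 12, or treatment failure. The agreement is reported, and the primary study ophthalmologist's reading is used in the primary analysis.

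**The concern.** A tolerance of one level suits a scale with several grades. Applied to a yes/no reading, it accepts every possible answer. An investigator who contradicted the reference grader on lesions in all 5 patients would meet that part of the test, both at the start and at each yearly repeat.

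The lesion reading matters because an active lesion in one eye makes a patient a failure at month 6 whatever the cells and haze show. It matters most in posterior uveitis and panuveitis, which form one side of the prespecified anatomic subgroup analysis (SAP 3.2.2).

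No later step corrects a wrong reading. Protocol 5.3.3 sets no agreement threshold and no adjudication for the duplicate gradings. The reading center's listed tasks (Protocol 9.11 and 10.3) are vitreous haze, macular edema type, epiretinal membrane and image quality, not lesion activity.

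**Working it through.** The plan gives no figure to reproduce here, so the check is logical, with a little arithmetic on the alternative rule.

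**Inputs.** The tolerance is one level and the run is 5 consecutive counted patients (Protocol 5.3.4). The lesion reading has 2 levels (SAP 3.1; Protocol 2.3.2 and Table 2). Cells and haze have 6 grades each (Protocol 5.3.2), each counted as one step. Agreement rates for lesion readings are not in the documents; those used below are assumptions.

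**Step 1: can the rule be breached?** With L levels there are L × L pairs of readings by two graders. A breach needs a difference of at least 2 steps. The number of such pairs is L² − L − 2(L − 1).

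| Reading | Levels | Largest difference | Pairs that breach |
|---|---|---|---|
| Lesions, active or not | 2 | 1 | 4 − 2 − 2 = 0 of 4 |
| Lesions, if none/mild/severe | 3 | 2 | 9 − 3 − 4 = 2 of 9 |
| Cells or haze | 6 | 5 | 36 − 6 − 10 = 20 of 36 |

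On the yes/no reading the chance of meeting the lesion criterion is 1 at any agreement rate, including 0%. Under exact agreement, 2 of the 4 pairs would breach.

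**Step 2: would a severity split rescue the rule?** On a none/mild/severe scale the only breaching pairs are none against severe, in either order. None against mild would still pass, and that disagreement already changes not active to active.

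**Step 3: what would exact agreement do in the first 5 patients?** With agreement rate a per patient, P(no lesion breach in 5) = a⁵:

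- a = 0.50: 0.03
- a = 0.70: 0.17
- a = 0.80: 0.33
- a = 0.90: 0.59
- a = 0.95: 0.77

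**Step 4: how many patients until certified?** Protocol 5.3.4 continues until a run of 5 is reached, so the a⁵ values are first-attempt rates, not final ones. For the lesion item alone, the mean number of patients to the first run of 5 agreements is (1 − a⁵)/((1 − a)a⁵):

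- a = 0.95: 0.2262/(0.05 × 0.7738) = 5.8
- a = 0.90: 0.4095/(0.10 × 0.5905) = 6.9
- a = 0.50: 0.96875/(0.50 × 0.03125) = 62

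Exact agreement would thus certify good graders quickly and hold back only poor ones.

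**Step 5: which patients count?** A patient counts if either grader finds inflammation in any area. All 5 could have cells or haze and no active lesion. An exact-agreement rule therefore also needs a condition on the mix of cases.

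**The case against.** **Other safeguards exist.** Protocol 5.3.4 also requires a review of the classification system with all investigators and an exam score of 80%. Protocol 5.3.2 points to ancillary imaging and a disease-specific table in Appendix F, and says that vasculitis should be confirmed by angiogram. Examiners are uveitis specialists, and Protocol 9.1 asks for the same ophthalmologist across a patient's visits. This stands: a reader might infer that certification leaves the lesion reading wholly unchecked, and the documents do not support that. None of these steps, however, compares two graders' lesion readings against a pass mark.

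**The forms might hold a graded scale.** The eye exam and certification forms (Appendices A and B) are not in the text, and 5.3.4 speaks of grades for every area. A multi-level field cannot be excluded. The text of the protocol and SAP defines none for certification or for the endpoint. The mild/severe wording in 3.2.1 is discretionary and concerns reactivation.

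**A loss of power.** A reader might infer that power falls below the planned 80% by some calculable amount. The documents do not support this. They give no lesion error rate and no share of failures that rest on lesions alone. Any such figure would compare assumed error with none, whereas planning rates drawn from earlier studies presumably already contain reading error. Nor could the loss be put down to this rule: by Step 4, a grader with 90% agreement would be certified under exact agreement too, after about 7 patients on average.

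**Cells and haze have a threshold problem too.** A reading of 0.5+ against 1+ crosses the limit for control and is tolerated. That is true, but the test on those scales can still fail an examiner whose readings are further off. The lesion test can fail nobody.

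**Conclusion.** Wrong as written, low severity. For retinal/choroidal lesions the hands-on agreement test is met by every possible set of readings, so it cannot detect disagreement on this component of the primary endpoint. This rests on one premise, that the lesion reading is active versus not active, which the protocol and SAP text support consistently.

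The point is confined to the lesion component. An investigator can still be held back on cells, haze or the exam. No bias between arms is claimed, since the examiners are masked to treatment. The effect on power cannot be quantified from the documents and no power figure is claimed. Sample size and alpha are unaffected.

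**What to change.** In Protocol 5.3.4, give retinal/choroidal lesions, including vasculitis posterior to the equator, their own criterion: exact agreement with the reference grader on active versus not active in each of the 5 consecutive counted patients. At least one of the 5 should be read as active and at least one as not active by the reference grader, so that an examiner who always gives the same answer cannot pass. Apply the criterion at initial and yearly certification.

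If a multi-level lesion scale is intended, cite it in 5.3.4 and require agreement on the cut between active and not active.

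The change takes a sentence or two in the manual and an edit to the certification form. The cost is that some investigators will grade a few more patients before they are certified, partly to obtain the required mix of cases.

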5.4. Optical coherence tomography

We will be using spectral-domain optical coherence tomography (SD-OCT) in this study to monitor the effects of treatment by measuring macular thickness and changes in macular thickness. We will be utilizing the Heidelberg Spectralis SD-OCT unit for all study assessments. Each site must have access to the Heidelberg Spectralis unit at the time of study initiation and must continue to use that same scanner for all patients for the duration of the study. If Heidelberg Spectralis is not available, the Zeiss Cirrus SD-OCT may be used.

5.4.1. Required patient assessments—Heidelberg Spectralis

For our study, one of each of the following scans is required for each eye:

- **20° x 20° High Speed Volume scan centered on the macula**
 - 20° x 20°
 - 49 sections
 - 16 frames (ART)
- **7-Lines scan centered on the macula**
 - 30° x 5°
 - 7 sections
 - 25 frames (ART)

5.4.2. Scan procedures—Heidelberg Spectralis

Procedures for Obtaining Scans

General Guidelines

- Scans may be obtained if the patient's pupils are not dilated. However, pupil dilation prior to obtaining scans is encouraged
- Clean chin rest and forehead rests
- Adjust table and chin rest height to ensure patient comfort
- Make sure that patient is aligned straight; slight face turns to the left or right may decrease scan quality

Click on the Preset “**Dense**” scan icon on the screen to obtain the 20° x 20° volume scan. Please make sure that the scan will have the following parameters:

- 20° x 20°
 - 49 sections
 - 16 frames (ART)
- Pull the camera all the way back
 - Move the instrument toward the patient slowly, taking care not to alarm patient and to not touch the patient’s eyes or eyelashes with the instrument
 - Ask patient to fixate on the blue light on the inside of the machine
 - Remind patient not to follow the movement of the red scan lines
 - If patient is having trouble focusing on fixation light, you may need to help the patient direct his/her gaze by using external fixation targets
 - Focus in on the circular black and white retinal reflex
 - Move the camera forward so that the fundus image comes into view and fills the screen
 - Use the focusing knob to obtain maximum brightness and clarity of the image
 - Ensure that the image is maintained in the **upper third** of the screen
 - Click “Acquire”
 - Repeat for next eye

Click on the “**7 Lines**” Preset Scan icon

This scan will have the following parameters:

- 30° x 5°
 - 7 sections
 - 25 frames (ART)
- Focus image as described above
 - Click “Acquire”
 - Repeat for next eye
 - **Please review scans for completeness and quality. A good quality scan should have a score of at least 20. Please repeat any scans that are not complete or of poor quality.**

5.4.3. Obtaining retinal thickness data—Heidelberg Spectralis

- After closing the acquisition window, double click on the volume scan.
- Select “Thickness Map” tab
- Record central subfield thickness of each eye on data sheet
- Print out copy of scan for patient file

Be sure to complete analysis of data and record information on data collection form as soon as possible. This will ensure that the treating physician will be able to use the SD-OCT results in real time to determine if macular edema is present or not.

